QOL-B respiratory domain scores are measured on a scale from 0 to 100 (with higher scores indicating better health-related quality of life). QOL-B respiratory domain scores will be summarized by visit in the Micro-ITT Population. Descriptive statistics of both the reported QOL-B respiratory domain scores and change from baseline will be reported by visit (monthly through Month 6). Change from baseline to Month 6 in QOL-B respiratory domain score will be analyzed using an analysis of covariance (ANCOVA) model, including baseline score, treatment and either including (primary analysis) or excluding (sensitivity analysis 1) stratification factors of baseline ALIS use and the presence or absence of any fibrocavitary disease as covariates. Least squares means, 95% confidence intervals, and p-values of the treatment comparison will be presented for both the Micro-ITT (primary) and PP (sensitivity) populations.

Patients who fail to provide a complete QOL-B respiratory domain score at both baseline and Month 6 will be excluded from the analysis and considered unbiased under the missing at random (MAR) assumption, with the exception of patients experiencing intercurrent events, which will be accounted for following the imputation rules above. However, in an additional pair of sensitivity analyses, the primary efficacy analysis will be repeated as described above, but applying a treatment policy strategy in which results for patients with new, additional non-study-specific, antimycobacterial therapy that is potentially effective against MAC, or surgery for MAC lung disease, for reasons other than clinical failure of study drug, will be used as recorded. These models will be run using the ANCOVA model as described above, including baseline score, treatment and either including (sensitivity analysis 2) or excluding (sensitivity analysis 3) stratification factors of baseline ALIS use and the presence or absence of any fibrocavitary disease as covariates.

3.4.3.2 Phase 3 Primary Efficacy Endpoint Outside the US (Key Secondary Endpoint in the US)

The primary efficacy outside the US (secondary in the US) is by-patient sputum culture conversion monthly through Month 6. The Estimand corresponding to the primary endpoint is defined with the following five attributes:

1. Population: Patients with MAC culture-positive Pre-Study and Screening respiratory specimens

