3.4.3.4 Phase 3 Exploratory Efficacy Endpoints

In an exploratory analysis, descriptive statistics for least-square mean difference of change from baseline in QOL-B respiratory domain score and MACrO₂ total scaled score, and by-patient sputum culture conversion by Month 6 will be presented by age category, ALIS use at baseline, presence-absence of any fibrocavitary disease, chest cavity category (non-cavitary, cavity diameter ≤ 3 cm, cavity diameter > 3 cm from EDC), MAC resistance phenotype (ie, macrolide-resistant, amikacin IV-resistant, and amikacin (liposomal, inhaled)-resistant), sex, baseline creatinine clearance category (<60 mL/min, ≥60 mL/min to <90 mL/min, or ≥ 90 mL/min), BMI category (<18.5 vs ≥18.5 kg/m²), and country of enrollment in the Micro-ITT Population. Forest plots of the estimated treatment difference and 95% confidence interval will be presented across all subsets, but no formal statistical testing will be performed.

Change from baseline in continuous PROs, including QOL-B respiratory domain score, MACrO₂ total scaled score, NTM Symptoms Module Domain score, and SGRQ-C total score, will be analyzed using a mixed model for repeated measures (MMRM) that includes randomized treatment, visit (from Baseline to Month 6 inclusive), and treatment by visit interaction as explanatory variables, and corresponding baseline score as a continuous covariate. Treatment visit and treatment by visit interaction will be fixed effects in the model, and treatment by visit interaction will remain in the model regardless of significance. The participant effect will be fitted as a random effect and an unstructured covariance structure will be assumed for within participant variation. If this model does not converge then the covariance matrices of Toeplitz, first-order autoregressive, and compound symmetry will be used in that order until the model converges. The analysis will be performed using PROC MIXED in SAS and the resulting F-tests will be based on Kenward-Roger's adjusted degrees of freedom. Least squares means, 95% confidence intervals, and p-values of the treatment comparisons at Month 3 and Month 6 will be presented for both Micro-ITT and PP populations, along with an assessment of the difference between slopes from baseline to Month 6 and residual plots will be provided to examine departures from normality and/or outliers.

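### The Phase 3 exploratory MMRM applies one baseline slope to every visit, so its Month 6 estimate will generally differ from a Month 6 ANCOVA even with complete data; a baseline-by-visit term removes this at almost no cost

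*SAP*

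**What the plan says.** SAP section 3.4.3.4 (Phase 3 Exploratory Efficacy Endpoints) analyses change from baseline in the QOL-B respiratory domain, MACrO₂ total scaled score, NTM Symptoms domain and SGRQ-C total with an MMRM. The fixed effects begin with "randomized treatment, visit (from Baseline to Month 6 inclusive" and go on to "treatment by visit interaction as explanatory variables, and corresponding baseline score as a continuous covariate". No baseline-by-visit term and no stratification factor is listed. On covariance the section says: "The participant effect will be fitted as a random effect and an unstructured covariance structure will be assumed for within participant variation". Simpler structures follow if the model does not converge. The output is least squares means, intervals and "p-values of the treatment comparisons at Month 3 and Month 6 will be presented for both Micro-ITT and PP populations".

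The primary US analysis in section 3.4.3.1 is a separate Month 6 ANCOVA, "including baseline score, treatment and either including (primary analysis) or excluding (sensitivity analysis 1) stratification factors of baseline ALIS use" and fibrocavitary disease. On missing data it says: "Patients who fail to provide a complete QOL-B respiratory domain score at both baseline and Month 6 will be excluded from the analysis". The stated basis is missing at random.

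**The concern.** A main effect for baseline forces the same regression of change on baseline at Month 1 and at Month 6. If a patient's score drifts away from its baseline value over time, that regression steepens, and a slope averaged over visits is too shallow at Month 6. The baseline adjustment of the Month 6 treatment difference is then not the one the ANCOVA makes.

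What is at stake is interpretation rather than a formal decision. The primary ANCOVA drops patients without a Month 6 score. SAP section 3.1.4 promises a longitudinal analysis that uses all time points up to Month 6, and in Phase 3 this MMRM is what fits that description. It is the natural cross-check on the complete-case result. A reader who sees the two disagree would want to attribute the gap to missing data, not partly to a different baseline slope.

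**Working it through.** **The plan's own figures.** The documents give no SD, correlation or power for QOL-B or for the MMRM. The only Phase 3 power figure (SAP 2.2.7: 124 and 62 patients, 30% vs 10%, two-sided 0.05, about 90%) recomputes to 0.897. It concerns a responder endpoint and does not bear on this point.

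**Inputs.** From the documents: 124:62 patients in the planned Micro-ITT Population and six monthly post-baseline visits. Assumed: score SD 20, and the correlation structures below. The calculation uses Months 1 to 6 only.

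**Formulae.** Let b_t be the slope of change on baseline at month t. With constant SD, b_t = ρ_t − 1, where ρ_t is the correlation of the month t score with baseline. Let S be the residual covariance of the six changes given baseline, s6² its Month 6 variance, σx² the baseline variance and d the baseline difference between arms.

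- Common slope: c = Σ w_t b_t, with w = S⁻¹1 / (1′S⁻¹1).
- Gap between the estimates: common-slope estimate − ANCOVA estimate = (b6 − c) × d.
- Randomization makes the mean of d zero, so the gap adds no bias. It adds variance: ratio = 1 + (b6 − c)² σx² / s6².

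**Example, AR(1) 0.92.** ρ6 = 0.92⁶ = 0.606, so b6 = −0.394 and s6²/σx² = 1 − 0.606² = 0.632. The weights give c = −0.109. The variance ratio is 1 + 0.285²/0.632 = 1.129, and the SE ratio is √1.129 = 1.062.

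**All structures.** The simulation used 4,000 complete-data trials per row. Gaps are absolute differences from the ANCOVA without strata, in points.

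| Assumed correlation | b6 | c | SE ratio, large-sample | SE ratio, simulated | Mean gap (95th percentile) |
|---|---|---|---|---|---|
| AR(1) 0.92 | −0.394 | −0.109 | 1.062 | 1.056 | 0.73 (1.82) |
| AR(1) 0.85 | −0.623 | −0.236 | 1.084 | 1.080 | 0.99 (2.46) |
| Stable trait + decaying part + noise | −0.408 | −0.287 | 1.011 | 1.008 | 0.31 (0.84) |
| Constant 0.7 | −0.300 | −0.300 | 1.000 | 0.998 | 0.08 (0.27) |
| Random intercept and slope, slope unrelated to baseline | −0.294 | −0.294 | 1.000 | 0.997 | 0.10 (0.35) |

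If the correlation falls linearly with lag over six months, the large-sample SE ratio is 1.012 (0.70 to 0.50), 1.018 (0.70 to 0.45), 1.021 (0.75 to 0.50) and 1.029 (0.75 to 0.45).

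The two estimates differed in every simulated trial. Type I error of the common-slope model was 0.053 to 0.056.

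**Where the slope comes from.** Month 1 carries 90%, 78%, 44%, 17% and 32% of the weight in the five rows, and Months 1 to 3 carry 91%, 82%, 72%, 50% and 77%. The last row has heavy early weight and no loss, because its visit slopes are equal. Uneven weight matters only if the slopes differ.

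**What the added term does.** In one simulated data set (trait structure, d = 2.195) the Month 6 ANCOVA without strata gave −2.976 (SE 2.475). The MMRM with baseline-by-visit gave the same estimate and SE. The common-slope MMRM gave −3.098 with slope −0.311. The gap of −0.122 divided by 2.195 implies b6 − c = −0.056. The SE in that data set was 2.472, so a single trial need not show any loss.

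**The case against.** The strongest reply is that this is a valid, fully specified model and the extra term is a matter of preference. The MMRM is exploratory and outside the testing hierarchy in SAP section 3.4. It is unbiased with complete data and keeps its type I error, and the primary ANCOVA does not depend on it. All of that stands, and it limits the point to an optional improvement.

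Four stronger readings are tempting, and the documents do not support them:

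- **The slope is necessarily set by early visits and the estimate necessarily less precise.** Both depend on how correlation with baseline behaves, which the documents do not report. With equal visit slopes the simpler model is no worse. The 6 to 8% figures need pure AR(1) decay, with no stable component and no measurement noise, which is extreme for a questionnaire score.
- **The one added term would make the MMRM match the primary ANCOVA, so any remaining gap would be missing data.** The primary model contains ALIS use and fibrocavitary disease and the MMRM does not, so the term alone matches sensitivity analysis 1. Section 3.4.3.4 also does not restate the intercurrent-event rule of section 3.4.3.1, and a fallback covariance would generally give a different SE.
- **The MMRM is the only use of Months 1 to 5 scores for the Month 6 comparison.** Section 3.4.3.1 sets scores after new antimycobacterial therapy or lung surgery to the last earlier value, so earlier scores can enter the primary analysis. Section 3.1.4 also allows imputation analyses.
- **The Month 6 result is biased.** With complete data it is not. A deliberately severe dropout scenario, with dropout depending on baseline in opposite directions by arm, shifted the common-slope estimate by about 1.1 to 2.5 points relative to the visit-slope model. Neither model was biased under completely random dropout. This shows a mechanism and predicts nothing about this trial.

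**Conclusion.** The point holds as a small improvement that costs almost nothing. As written, the MMRM uses one baseline slope for all visits, and its Month 6 treatment difference will generally differ from a Month 6 ANCOVA even when no data are missing. Under the assumed SD of 20 and planned numbers, the mean absolute gap was 0.08 to 0.99 points.

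The precision loss is conditional. It is nil if correlation with baseline is constant, about 1 to 2% of the SE under most mixed structures (2.9% in the steepest linear decline tried) and at most about 8% under pure AR(1) decay. For scale, an effect sized for 90% power would have about 89% at an SE ratio of 1.011 and 85 to 86% at 1.062 to 1.084, although no formal test rests on this model.

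The trial was terminated early, so actual Phase 3 numbers may be below 186. That would change the absolute SEs and gaps but not the large-sample ratios. No primary or hierarchical conclusion is affected.

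**What to change.** Add the baseline score-by-visit interaction to the MMRM fixed effects for all four continuous PROs. This replaces one slope with six, so it costs five parameters and one model term, uses data already collected, and can be made before Phase 3 unblinding.

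Limit the response visits to Months 1 to 6, because the equality with the ANCOVA is derived for those visits. With complete data and the unstructured covariance, the Month 6 estimate and SE then equal sensitivity analysis 1.

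If agreement with the primary ANCOVA is the aim, also add ALIS use and fibrocavitary disease, each by visit: two binary factors over six visits, or 12 further parameters. State in section 3.4.3.4 whether the intercurrent-event rules of section 3.4.3.1 apply to the MMRM. The testing hierarchy and the primary analysis need no change.

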2.2 Study Design

2.2.1 Overview

Refer to Protocol Section 3.1 Summary of Study Design for full details of the study overview.

Briefly, this is a pivotal Phase 2/3, double-blind, placebo-controlled study of eptraborole + OBR versus placebo + OBR in patients with treatment-refractory MAC lung disease. This study will enroll adult patients with treatment-refractory MAC lung disease who meet all eligibility criteria.

This study features a sequential Phase 2/3 approach with an initial Phase 2 assessment of clinical responses (based on clinical symptoms and/or functional assessments), microbiological responses, safety, and PK associated with oral eptraborole, prior to the superiority analysis of oral eptraborole versus placebo in the Phase 3 part of the study.

In both the Phase 2 and Phase 3 parts of the study, each patient will complete multiple PRO measures including MACrO₂, QOL-B, NTM Symptoms Module, SGRQ-C, and global patient and clinician assessment scales (Patient Global Impression of Severity [PGIS], Patient Global Impression of Change [PGIC], Clinician Global Impression of Severity [CGIS], Clinician Global Impression of Change [CGIC]), and Meaningful Change Question (to be answered after each completion of the PGIC). An electronic PRO system will be used during the study to allow patients to complete the study questionnaires electronically.

The MACrO₂ PRO will be completed twice before the first dose of study drug to assess test-retest reliability (within 1 to 2 weeks prior to randomization, and on randomization day prior to study drug administration) and once weekly for the first 6 months of the study; other PROs and global assessment scales will be completed at baseline and once monthly for the first 6 months of the study. The QOL-B, NTM Symptoms Module, SGRQ-C, and PGIS will also be completed during Screening for test-retest reliability assessment. The PGIC, CGIC, and Meaningful Change Question will not be completed at baseline. After Month 6, all PROs will be completed every 3 months (84 days \pm 7 days), at End of Therapy (EOT), and at Late Follow Up (LFU). Sputum samples for microbiological assessments will be collected during the Screening period, once monthly for the first 6 months of the study, and then every 3 months (84 days \pm 7 days), at EOT, and at LFU.

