3 STATISTICAL METHODOLOGY

3.1 General Considerations

3.1.1 Analysis Day

Study days are calendar days, rather than 24-hour days. Analysis day will be calculated from the date of first dose of study drug. The day of the first dose of study drug will be Day 1, and the day immediately before Day 1 will be Day -1. There will be no Day 0. Any durations in days will be derived as event stop date – event start date + 1.

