By-patient sputum culture conversion by Month 6 and by-patient microbiological improvement at Month 3 and Month 6 by epetaborole MIC across all baseline pathogens and within each individual baseline pathogen species will be summarized by treatment group in the Micro-ITT Population. By-pathogen microbiological sputum culture conversion at Month 6 and by-pathogen microbiological improvement at Month 3 and Month 6 will be summarized by treatment group for each individual baseline pathogen in the Micro-ITT Population.

Time (in days) to first sustained improvement in QOL-B respiratory domain score by a threshold (11.1 points) determined as part of a blinded anchor-based psychometric analysis of pooled Phase 2 data, time (in days) to first sustained MACrO₂ PRO-based clinical response through Month 6, and time to first sustained improvement in MACrO₂ total scaled score by a threshold (11.3 points) determined as part of a blinded anchor-based psychometric analysis of pooled Phase 2 data will be summarized by treatment group in the Micro-ITT Population. The first sustained PRO-based clinical response through Month 6 is defined as the earliest study day at which the weekly (or monthly) PRO assessment meets the criteria of clinical response and which is maintained consistently at all available subsequent assessments through Month 6 (inclusive). Missing assessments will be excluded from sustained response determination. A Kaplan-Meier analysis and corresponding plot will be provided by treatment, and estimated event rates by treatment arm based on the plot will be provided for study days 29, 57, 85, 113, 141, and 169 to align with protocol specified visit months. Patients who fail to achieve sustained response by Month 6 or discontinue early from the study will be censored at their last day of treatment or the day of their Month 6 visit, whichever is earlier. In an alternative approach to assess the impact of censoring on the analysis results, the same analysis will be performed where all patients who fail to achieve sustained response and who discontinue from the study prior to Month 6 will be censored at the maximum allowable duration of 6 Months. Time to event will also be analyzed using a Cox proportional hazard model with the same variables as the previous exploratory analysis, and hazard ratio and 95% confidence intervals at Month 6 will be reported.

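### The Kaplan-Meier rules for time to first sustained QOL-B improvement mix actual visit days with nominal read-out days, so Month 1 to 5 rates run low, the Day 169 rate is biased either way, and the curve overshoots after Day 169.

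*SAP*

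**What the plan says.** SAP 3.4.3.4 adds this Phase 3 endpoint: "Time (in days) to first sustained improvement in QOL-B respiratory domain score by a threshold (11.1 points", with the threshold taken from blinded Phase 2 psychometric work. The event day is "the earliest study day at which the weekly (or monthly) PRO assessment meets the criteria of clinical response", provided the response is one "which is maintained consistently at all available subsequent assessments through Month 6 (inclusive". SAP 3.1.1 adds "Analysis day will be calculated from the date of first dose of study drug". Nothing in the SAP maps visits to nominal days for this analysis.

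SAP 2.2.1 sets the frequency for instruments other than MACrO₂: "other PROs and global assessment scales will be completed at baseline and once monthly for the first 6 months of the study". Protocol 3.1 and Appendix A Table 3 place those visits every 28 days with a window of 7 days either side, so Month 6 covers Days 162 to 176.

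Patients without sustained response "will be censored at their last day of treatment or the day of their Month 6 visit, whichever is earlier". The read-out rule is that "estimated event rates by treatment arm based on the plot will be provided for study days 29, 57, 85, 113, 141, and 169", and its stated purpose is "to align with protocol specified visit months". A second analysis moves the censoring time only for patients who leave the study before Month 6.

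**The concern.** QOL-B events can be observed only on visit days. Two features of the rule then work against its stated aim of describing the visit months.

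First, a Month 1 event recorded on Days 30 to 36 is absent from the Day 29 rate. The next visit window opens only on Day 50, so no early Month 2 event makes up for it.

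Second, at Month 6 the same assessment decides both whether a patient has an event and whether the patient is censored. From Day 162 onward, assessed non-responders leave the risk set while unassessed patients remain. Later events are divided by an ever smaller group. The censoring is therefore tied to the outcome, and it operates even with complete data.

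At stake is whether the tabulated rates and the plotted curve describe the proportion with sustained response by each month.

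**Working it through.** The SAP states no Kaplan-Meier rate, so there is no planned figure to reproduce. The read-out days are 1 + 28k for k = 1 to 6, that is 29, 57, 85, 113, 141 and 169.

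**Inputs from the documents:** event, censoring and read-out rules (SAP 3.4.3.4); window of ±7 days (Protocol 3.1).

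**Assumed, because the documents do not give them:** the spread of visit days within the window and the pattern of first sustained response. The main scenario takes QOL-B change with mean 5, SD 15 and between-visit correlation 0.6. No dropout. Events are counted before censorings on the same day.

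**Comparator:** cumulative share of patients whose first sustained response is at or before each monthly visit. In the main scenario this is 8.2, 9.6, 11.6, 14.8, 20.6 and 34.2%.

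**1. Months 1 to 5.** Reported rate = previous month's cumulative rate + that month's increment × share of visits on or before the nominal day. With uniform visit days the share is 8/15, so 7/15 = 47% of each increment is not yet counted.
- Month 1: 8.2 × 8/15 = 4.4%
- Month 2: 8.2 + 1.4 × 8/15 = 8.9 to 9.0%, depending on rounding of the inputs
- Month 3: 9.6 + 2.0 × 8/15 = 10.7%
- Month 4: 11.6 + 3.2 × 8/15 = 13.3%
- Month 5: 14.8 + 5.8 × 8/15 = 17.9%

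The relative loss at Day 29 is simply the share of late visits: 43 to 47% for uniform or normal SD 3 spreads, but 20% if 60% of visits fall on the nominal day and the rest are spread evenly.

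**2. Month 6.** Let p be the chance that a patient still at risk has a first sustained response at Month 6, w(d) the share of Month 6 visits on day d, and T(d) the share on day d or later. If non-responders are censored on their visit day, the Month 6 increment by day t is

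1 − ∏ over d = 162..t of [1 − p·w(d)/T(d)],

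which for uniform days is 1 − ∏ [1 − p/(177 − d)]. For a true increment of p = 10%:

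| Month 6 visit spread | By Day 169 | By Day 176 |
|---|---|---|
| Uniform | 7.0% | 28.8% |
| 60% on nominal day, rest even | 9.5% | 30.7% |
| Normal, mean 0, SD 3 | 7.5% | 37.2% |
| Normal, one day early, SD 3 | 10.0% | 40.6% |
| Normal, two days early, SD 3 | 12.9% | 44.0% |

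Two errors oppose each other at Day 169: late events are missed, and the risk set has already shrunk. In a continuous approximation with small p, the increment by day t is p × [−ln(1 − F(t))], where F is the share of visits done by t. This equals p when F = 1 − 1/e, about 63%. Below that the Day 169 rate is low; above it, high. After Day 169 only the shrinking risk set matters, so the curve rises too far in every row.

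**3. Main scenario, Month 6.** p = (34.2 − 20.6)/(100 − 20.6) = 0.171. Uniform days give 1 − 0.794 × ∏ = 29.9% at Day 169 and 56.1% at the end of the curve, against 34.2%. Normal SD 3 gives 30.5% and 64.8%. Visits two or three days early on average give 37.5% and 41.5% at Day 169, which is too high.

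**4. Range.** Over four response patterns and the two symmetric spreads, Day 169 is 1.2 to 5.1 points low, and the curve ends at 40 to 74% against visit-based rates of 25 to 42%. Simulation of the main scenario at the planned arm size of 124, uniform days, gave 30.0% at Day 169 and 55.6% at the end, against 34.3%.

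**5. Last-dose branch.** Protocol 3.1.1 stops study drug at the Month 6 visit for patients who have not culture-converted. If the last dose of QOL-B non-responders is the day before the visit, they are censored before responders seen on the same day. In the main scenario Day 169 then runs from 30.7% (uniform) to 49.5% (60% on the nominal day), and the curve reaches 100% in large samples.

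**6. No-bias case.** If every visit is on its nominal day and no last dose is earlier, the rates are correct.

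**The case against.** The best case against acting is that little depends on this display. It is exploratory and outside the testing order in SAP 3.4. The steep overshoot lies after the last tabulated day, and the SAP asks for no median. With complete data, sustained response through Month 6 is the same as response at Month 6, and SAP 3.4.3.3 already reports that proportion at the 11.1-point threshold with a Miettinen-Nurminen interval. All of this stands, and it makes the point minor. It also means the study report could show different Month 6 figures for the same patients: 34.2%, 29.9% and a curve ending at 56.1% in the main scenario.

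A reader might infer that every monthly rate is too low. The documents do not support that for Day 169, because they give neither the visit spread nor the timing of last doses, and early visits reverse the sign.

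A reader might also infer a biased treatment comparison. Both arms share one blinded schedule and one rule. A simulated Cox model with complete data and uniform visits gave a hazard ratio of 1.62 (95% CI 1.55 to 1.69) on actual days and 1.58 (1.51 to 1.65) on nominal days, which are compatible.

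The planned alternative censoring does not answer the point: completers without response stay censored on their own day.

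**Conclusion.** The concern holds in a limited form. With little dropout, the Month 1 to 5 rates are too low whenever some visits run late, and the shortfall is that month's increment times the share of late visits. The Day 169 rate is biased in a direction set by visit and last-dose timing. It was low for the symmetric spreads tested, and can be unbiased or high if visits run early or last doses precede the visit. After Day 169 the curve rises far above the true proportion; this affects the plot and any quantile read from it, not the six tabulated rates.

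The mechanism follows from the SAP text. The sizes rest on assumed visit spreads and response patterns, and on complete data. The arm sizes simulated include the planned ones, although SAP 1 records that the trial was terminated early. No primary or hierarchical test is affected.

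**What to change.** In SAP 3.4.3.4, for PROs assessed monthly:
- set the event time to the nominal day of the visit at which sustained response first occurs;
- censor completers without response at Day 169;
- censor early discontinuers at the nominal day of their last assessment;
- keep the six read-out days and end the plot at Day 169.

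With complete data this returns the visit-based rates exactly (8.2, 9.6, 11.6, 14.8, 20.6 and 34.2% in the main scenario). The handling of early discontinuers was not tested and replaces the last-treatment-day rule for them. SAP 3.4.1.4 already defines one Phase 2 event, sustained decrease in colony count, by monthly visit, so visit-based timing is not foreign to the plan.

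The cost is a short text change and a new derivation of the time variable. Day-level timing is lost, but a monthly schedule does not support it. Extending the rule to weekly MACrO₂ by nominal week is optional and was not tested.
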